3.3 STUDY END POINTS

Primary end point

1. Change in frequency of daily stress urinary incontinence episodes from Baseline to Week 12.

Secondary end points

1. Change in frequency of daily voids from Baseline to Week 12.
2. Change in urine volume per void from Baseline to Week 12.
3. Change in 24 hour pad weight from Baseline to Week 12.
4. Change in maximum urethral closure pressure measurements from Baseline to Week 12.
5. Change in urine leakage (yes/no) on the Bladder Stress Test from Baseline to Week 12 as assessed while (a) coughing, and/or (b) performing a Valsalva maneuver.
6. Change in total score on the stress incontinence section of the MESA Urinary Questionnaire from Baseline to Week 12.
7. Change in Patient Global Impression of Severity (PGI-S) Scale from Baseline to Week 12.
8. Patient Global Impression of Improvement (PGI-I) Scale at Week 12.
9. Change in total score on the Urinary Distress Inventory (UDI-6) from Baseline to Week 12.
10. Change in total score on the Incontinence Impact Questionnaire (IIQ-7) from Baseline to Week 12.
11. Change in total score on the Female Sexual Function Index (FSFI) from Baseline to Week 12 as well as the change in subdomain scores: libido, arousal, lubrication, orgasm, satisfaction, and pain.
12. Change in pelvic floor muscles from Baseline to Week 12 as measured by MRI. Quantitative assessments may include the area of the levator hiatus, the anteroposterior and transverse diameters, and other relevant parameters.

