7.2 EARLY TERMINATION

Subjects may withdraw from the study voluntarily. In addition, if the PI determines that continued participation might present a safety risk for the subject then the PI may withdraw the subject from the study. Those subjects who receive study drug will be followed for 28 days after stopping study participation. Every effort will be made to obtain all end of treatment measures as outlined in (Table 1.Visit 6) in the event that a subject withdraws, or is withdrawn, from the study before completing treatment.

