10. STATISTICAL CONSIDERATIONS

Since this is a proof of concept feasibility study, no power calculation is needed. Based on Dalton, 2011, 10-20% of patients may withdraw from the study before completing treatment. Therefore, we will recruit up to 35 patients meeting inclusion/exclusion criteria until 30 subjects have completed treatment. Descriptive statistics will be used to explore changes in primary and secondary outcomes measures between baseline and end of treatment. Although the primary efficacy measure will be a change in frequency of daily stress leaks between Baseline and Week 14 weeks, response to treatment will also consider secondary efficacy measures (change in frequency of voids per day, urine volume per void, change in 24 hour pad weight, responses to validated questionnaires, changes in UPP measures, changes in sexual function), and change in pelvic floor muscles as measured by MRI. Safety will be reported by the number and type of adverse events reported during treatment. No imputations for missing data will be conducted. There will be no adjustment for multiple testing.

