10.1 STATISTICAL METHODS

Primary end point

- The average number of episodes per day of leaking (SUI) will be calculated by summing the number of episodes over the 3 day period and dividing by 3, the change from Baseline to Week 12 will be computed and this change will be summarized with descriptive statistics (min, max, median, mean, standard deviation) and analyzed for a significant change from Baseline using the Exact Wilcoxon sign rank test.

Secondary end points

- The average number of voids per day will be calculated by summing the number of voids over the 3 day period and dividing by 3, the change from Baseline to Week 12 will be computed and this change will be summarized with descriptive statistics (min, max, median, mean, standard deviation) and analyzed for a significant change from Baseline using the Exact Wilcoxon sign rank test.
- The average volume per void will be calculated by summing the total urine amount over the 3 day period and dividing by the total number of voids recorded over 3 days, the change from Baseline to Week 12 will be computed and this

change will be summarized with descriptive statistics (min, max, median, mean, standard deviation) and analyzed for a significant change from Baseline using the Exact Wilcoxon sign rank test.

- Change in maximum urethral closure pressure measurements from Baseline to Week 12 will be computed and this change will be summarized with descriptive statistics (min, max, median, mean, standard deviation) and analyzed for a significant change from Baseline using the Exact Wilcoxon sign rank test.
- Change in 24 hour pad weight from Baseline to Week 12 will be computed and this change will be summarized with descriptive statistics (min, max, median, mean, standard deviation) and analyzed for a significant change from Baseline using the Exact Wilcoxon sign rank test.
- Change in total score on the stress incontinence section of the MESA Urinary Questionnaire from Baseline to Week 12 will be computed and this change will be summarized with descriptive statistics (min, max, median, mean, standard deviation) and analyzed for a significant change from Baseline using the Exact Wilcoxon sign rank test.

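### The primary Week 12 result includes only women with a Week 12 diary, so it is an unlabelled completer estimate, and no fixed analysis shows the Week 12 change in all dosed women

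*Combined protocol and SAP*

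**What the plan says.** The primary end point in Section 3.3 is "Change in frequency of daily stress urinary incontinence episodes from Baseline to Week 12". Section 10.1 averages stress episodes over the 3-day diary. It then says "the change from Baseline to Week 12 will be computed and this change will be summarized with descriptive statistics", and that the change is "analyzed for a significant change from Baseline using the Exact Wilcoxon sign rank test".

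On missing data, Section 10 says "No imputations for missing data will be conducted". The same section expects that "10-20% of patients may withdraw from the study before completing treatment", and therefore "we will recruit up to 35 patients meeting inclusion/exclusion criteria until 30 subjects have completed treatment". It also speaks of using descriptive statistics to "explore changes in primary and secondary outcomes measures between baseline and end of treatment", and at one point dates the primary change to Week 14.

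No analysis population is defined, and no rule assigns any other diary to Week 12.

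For women who stop early, Section 7.2 says "Every effort will be made to obtain all end of treatment measures", but the sentence goes on to cite Visit 6 in Table 1 (Schedule of Measures). Visit 6 is the Week 16 telephone and mail contact, and Table 1 marks no voiding diary there. The end-of-treatment diary is at Visit 5.

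The exploratory part of Section 10.1 adds three things: changes at visits before Week 12, a mixed model over all available assessments that estimates a slope, and possible imputation by unnamed methods if the other analyses look encouraging. The protocol summary in Section 1 also mentions possible imputation, without that condition.

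**The concern.** A woman who stops before Week 12 leaves no primary value, so the headline result describes the women who stayed. Section 5.4.1 lets a woman leave whenever she wishes and lists intolerance and non-compliance among the reasons for withdrawal. Section 6.7 allows withdrawal for repeated poor compliance. In an unblinded study, staying may well go with perceived benefit or good tolerability. There is no control arm in which such selection could partly cancel.

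The stake is the proof-of-concept estimate itself. The Week 12 change is the main efficacy figure, and nothing planned for certain shows how far it depends on who stayed.

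**Working it through.** **1. The plan's own figure.** To obtain 30 completers with withdrawal share d, the number needed is 30/(1 − d).

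- d = 10%: 30/0.90 = 33.3, so 34.
- d = 15%: 30/0.85 = 35.3, so 36.
- d = 20%: 30/0.80 = 37.5, so 38.

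The ceiling of 35 corresponds to d = 1 − 30/35 = 14.3%, inside the stated range. If 35 are enrolled, the expected number of completers is 31.5, 29.75 or 28. The binomial chance of at least 30 is 0.87, 0.57 or 0.27. Between 3.5 and 7 women would be expected to have no primary value.

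**2. Size of the possible bias.** The documents give no outcomes for withdrawn women. Let r be their mean change as a fraction of the completers' mean change (an assumption). Then:

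all-treated mean = completer mean × [(1 − d) + d·r]

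overstatement = 1/[(1 − d) + d·r] − 1

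| r (assumed) | d = 10% | d = 5/35 = 14.3% | d = 20% |
|---|---|---|---|
| −0.25 (slightly worse) | 14.3% | 21.7% | 33.3% |
| 0 (no change) | 11.1% | 16.7% | 25.0% |
| 0.5 (half the benefit) | 5.3% | 7.7% | 11.1% |
| 1 (same benefit) | 0% | 0% | 0% |

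For example, d = 20% and r = 0 gives 1/0.80 − 1 = 25%.

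**3. The bias against sampling error.** Assume baseline is uniform on 4 to 15 episodes/day (mean 9.5, variance 11²/12 = 10.08), with an independent fall of 41% (SD 35 points).

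- Completers' mean fall: 9.5 × 0.41 = 3.895 episodes/day.
- Variance: (9.5² + 10.08) × (0.41² + 0.35²) − 3.895² = 100.33 × 0.2906 − 15.17 = 13.99, so SD = 3.74.
- With r = 0 and 4, 5 or 7 of 35 withdrawn, the bias is 3.895 × 4/35 = 0.45, 3.895 × 5/35 = 0.56 or 3.895 × 7/35 = 0.78 episodes/day.
- The completer standard error is 3.74/√31 = 0.67, 3.74/√30 = 0.68 or 3.74/√28 = 0.71.

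Only the 20% case exceeds one standard error. At r = 0.5 the bias halves.

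**4. What the other planned analyses supply.**

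- Changes at Weeks 4 and 8 include women who withdraw later, but they are not Week 12 changes.
- The mixed model uses those women's diaries, but its output is a slope. A slope converts to a Week 12 change only if the course over time is linear.
- Imputation is optional, names no method and depends on encouraging results, so it cannot be counted on as a check.

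**The case against.** The strongest reply is that the study is a small, uncontrolled, descriptive proof of concept without a power calculation. The placebo falls of 27% and 41% cited in Section 2.1 are a larger threat to interpretation than this selection. That stands, and it limits the point to an improvement. No confirmatory conclusion is at risk.

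The reply also corrects several stronger readings that a reader might reach:

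- **That withdrawn women's data are ignored.** They are not. Section 10.1 commits to a mixed model over all available assessments and to analysing the earlier visits. The gap is that neither gives a Week 12 change.
- **That early-termination diaries are collected and then discarded.** Section 7.2 cites a visit with no diary, so such diaries may not exist. No rule excludes them either, and the end-of-treatment wording in Section 10 could be read to admit them.
- **That the plan carries the completer effect into future sample sizes.** Section 10.1 ties future sizing to imputed estimates. The weakness is the condition attached to them.
- **That the analysis contradicts the objective.** Section 3.1 speaks of the effect of 12 weeks of treatment and does not specify all treated women. A completer result is a defensible reading, provided it is labelled as such.

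**Conclusion.** The point holds as a request for labelling and one fixed companion analysis. The primary summary and test rest on women with a Week 12 diary, while the plan itself expects one in ten to one in five to withdraw.

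Optimism is likely but not established. A reader might infer that the estimate must be biased towards benefit. The documents do not support that, because they report no outcomes for withdrawn women, and some reasons for leaving, such as an asymptomatic ALT rise, need not track leakage.

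The 11% to 25% range depends on assuming no change in withdrawn women, and the 5% to 11% range on assuming half the benefit. With equal benefit there is no bias. The size is modest against sampling error except near 20% withdrawal, but it cannot be judged from the results as now planned.

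**What to change.** 1. In Section 10.1, label the observed Week 12 summary and signed-rank test as the completer estimate.
2. Beside it, pre-specify one analysis of all dosed women with a baseline diary, run whatever the result. Fit the mixed model already planned, with visit as a categorical factor and the baseline diary as one of the repeated outcomes, so that a woman with only a baseline diary stays in. Use all Week 4, 8 and 12 diaries, and report the Week 12 mean change with its confidence interval.
3. Add a conservative bound that gives zero change to each woman without a Week 12 diary. Keep zeros in the ranking (Pratt method), because the usual signed-rank test drops zeros and would remove these women again.
4. Replace the condition that imputation follows only from encouraging results. Quote the range between these estimates when planning later trials.
5. Reconcile Section 7.2, which asks for end-of-treatment measures but cites Visit 6, with the Visit 5 diary in Table 1. State how an early-termination diary enters the analysis. Reconcile Week 14 and the end-of-treatment wording in Section 10 with Week 12 in Sections 3.3 and 10.1.

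The cost is one extra table and some wording. Items 2 and 3 use diaries already scheduled. The downsides are a possibly less favourable figure, a missing-at-random assumption in the mixed model, and a bound that is deliberately severe: it scores a woman who had improved by Week 8 as unchanged. For that reason it should stand as a bound and not as the main all-treated estimate.

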10.1 STATISTICAL METHODS

Primary end point

- The average number of episodes per day of leaking (SUI) will be calculated by summing the number of episodes over the 3 day period and dividing by 3, the change from Baseline to Week 12 will be computed and this change will be summarized with descriptive statistics (min, max, median, mean, standard deviation) and analyzed for a significant change from Baseline using the Exact Wilcoxon sign rank test.

Secondary end points

- The average number of voids per day will be calculated by summing the number of voids over the 3 day period and dividing by 3, the change from Baseline to Week 12 will be computed and this change will be summarized with descriptive statistics (min, max, median, mean, standard deviation) and analyzed for a significant change from Baseline using the Exact Wilcoxon sign rank test.
- The average volume per void will be calculated by summing the total urine amount over the 3 day period and dividing by the total number of voids recorded over 3 days, the change from Baseline to Week 12 will be computed and this

change will be summarized with descriptive statistics (min, max, median, mean, standard deviation) and analyzed for a significant change from Baseline using the Exact Wilcoxon sign rank test.

- Change in maximum urethral closure pressure measurements from Baseline to Week 12 will be computed and this change will be summarized with descriptive statistics (min, max, median, mean, standard deviation) and analyzed for a significant change from Baseline using the Exact Wilcoxon sign rank test.
- Change in 24 hour pad weight from Baseline to Week 12 will be computed and this change will be summarized with descriptive statistics (min, max, median, mean, standard deviation) and analyzed for a significant change from Baseline using the Exact Wilcoxon sign rank test.
- Change in total score on the stress incontinence section of the MESA Urinary Questionnaire from Baseline to Week 12 will be computed and this change will be summarized with descriptive statistics (min, max, median, mean, standard deviation) and analyzed for a significant change from Baseline using the Exact Wilcoxon sign rank test.
- Change in Patient Global Impression of Severity (PGI-S) Scale from Baseline to Week 12 will be computed and this change will be summarized with descriptive statistics (min, max, median, mean, standard deviation) and analyzed for a significant change from Baseline using the Exact Wilcoxon sign rank test.
- Patient Global Impression of Improvement (PGI-I) Scale at Week 12. Descriptive statistics, (min, max, median, mean, standard deviation) will summarize these scores.
- Change in total score on the Urinary Distress Inventory (UDI-6) from Baseline to Week 12 will be computed and this change will be summarized with descriptive statistics (min, max, median, mean, standard deviation) and analyzed for a significant change from Baseline using the Exact Wilcoxon sign rank test.
- Change in total score on the Incontinence Impact Questionnaire (IIQ-7) from Baseline to Week 12 will be computed and this change will be summarized with descriptive statistics (min, max, median, mean, standard deviation) and analyzed for a significant change from Baseline using the Exact Wilcoxon sign rank test.
- Change in total score on the Female Sexual Function Index (FSFI) as well as the change in subdomain scores: libido, arousal, lubrication, orgasm, satisfaction, and pain from Baseline to Week 12 will be computed and these changes will be summarized with descriptive statistics (min, max, median, mean, standard deviation) and analyzed for a significant change from Baseline using the Exact Wilcoxon sign rank test.

- Changes in pelvic floor muscles from Baseline to Week 12 will be summarized with descriptive statistics (min, max, median, mean, standard deviation) and analyzed for a significant change from Baseline using the Exact Wilcoxon sign rank test.
- Qualitative changes in pelvic muscles will be described as decreased, increased or no change at Week 12 relative to Baseline.

Exploratory Analyses

Changes from baseline to each of the assessment times prior to Week 12 for the above endpoints will be explored, described and tested for significance using the same analytical methods noted for the primary and secondary objectives above. Durability treatment will be assessed by evaluating changes in study measures between week 12 and 16 (end of study). There will be no adjustment for multiple testing, nor will any data be imputed.

Repeated measures (mixed models) will be used to examine the change over time by incorporating all available assessment times to test for a significant non-zero slope over time and estimate that slope and its standard error.

Various imputation methods may be explored if any of the above analyses indicate promise for the compound in the treatment of SUI. These imputation methods may allow for better estimation of effect size and consequently sample size estimation in future trials.

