Statistical Considerations:	
This is a proof of concept feasibility study, so no power calculation is needed. Therefore, up to 35 subjects meeting inclusion/exclusion criteria will be recruited until 30 subjects have completed treatment. Descriptive statistics will be performed to explore changes in primary and secondary outcomes measures between baseline and end of treatment. The primary efficacy measure will be a reduction in the number of stress incontinence episodes/day. Secondary efficacy measures will include reduction in number of voids per day, volume of voids, 24 hour pad weight, responses to validated questionnaires, changes in UPP measures, changes in sexual function, and changes in pelvic floor muscles as measured by MRI.
 
Safety will be determined by the number and type of adverse events reported during treatment. Various imputation methods may be explored.

Study Intervention/Treatment:	
Participation in this study includes 5 in person study visits and two telephone and/or mailed questionnaire visits. Additional in person and/or telephone visits may be added as needed.
 
Study subjects will receive 3 mg of GTx-024 orally daily.

Table 1. Schedule of Measures.

	Screening Visit Days -21-0	Additional Screening Days -21-0	Visit 1. Baseline³ Week 0	Visit 2. Week 1 ± 3 days	Visit 3. Week 4 ± 3 days	Visit 4. Week 8 ± 3 days	Visit 5. Week 12 ± 3 days	Visit 6. Week 16 ± 7 days
	Clinic Visit	Clinic Visit	Clinic Visit	Phone Call	Clinic Visit	Clinic Visit	Clinic Visit	Phone Call and Mail
Consent	x							
Inclusion/Exclusion	x		x					
History			x					
Interview/Vital Signs	x		x		x	x	x	
Height/Weight	x				x	x	x	
24 hour Pad Weight	Instruct		x		x	x	x	
3 day Voiding Diary	Instruct		x		x	x	x	
Serum AST, ALT, Total Bilirubin	x				x	x	x	
Serum FSH ¹ ,	x							
CBC			x				x	
UA Dipstick (with culture as needed)	x		x				x	
Lipid Panel			x				x	
Testosterone Levels			x				x	
SHBG			x				x	
UPP			x				x	
Pelvic MRI		x					x	
Bladder Stress Test	x						x	
Mammogram ²		x						
Begin Daily ⁴ Treatment			x					
End Treatment							x	
Concomitant Meds	x		x	x	x	x	x	x
Adverse Events			x	x	x	x	x	x
HIV, Hep A, B, C Testing	x							
UDI-6; IIQ			x		x	x	x	x
PGI-S			x		x	x	x	x
MESA Questionnaire	x				x	x	x	x
PGI-I					x	x	x	x
FSFI Questionnaire			x		x	x	x	x
Bladder Scan PVR			x		x	x	x	
Ciprofloxacin 500 mg po (or equivalent)			x				x	
Focused Physical Exam			x				x	

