Mammography is the process of using low-energy X-rays to examine the human breast, which is used as a diagnostic and screening tool. The goal of mammography is the early detection of breast cancer, typically through detection of characteristic masses and/or microcalcifications.

Magnetic Resonance Imaging(MRI)

MRI will be done at baseline and end of treatment to observe changes in pelvic floor muscles along with the thickness of the endometrium (mm). Quantitative assessments may include the area of the levator, the anteroposterior and transverse diameters, and/or other relevant parameters. Endometrial thickness can accurately be assessed by MRI (Stanislavsky, Weerakkody, et al., 2015; Nakamura et al., 2014); therefore, it is being used as a safety assessment in this study.

Medical, Epidemiological and Social Aspects of Aging (MESA) Questionnaire

The MESA questionnaire measures severity of specific types (stress, urgency, mixed) of urinary incontinence (UI). Two subscales, the urgency UI (6 items) and the stress UI (9 items). Test-retest reliability on “any incontinence” is high (agreement coefficient = .89). Validity (agreement between self-report on the MESA and clinician’s assessment) = 87% in women. The MESA questionnaire has demonstrated agreement on incontinence = 79% and 69% and 72% accuracy in predicting urodynamic diagnosis of stress UI and uninhibited detrusor contraction (Herzog, 1990a; Herzog, 1990b).

3 Day Voiding Diary

Subjects will record each episode of urinary leakage and record its severity. Subjects will also be asked to record urinary frequency, and urgency. Urine volume will also be recorded. 3 day bladder diaries are reliable measures of mean number of UI episodes/day, UI type, mean voids/24 hours, and mean voids during sleeping hours. 2-week test-retest results correlate with diurnal micturition ($r=.89$, $p<0.001$) and UI episodes ($r=.91$, $p<0.001$). Compared to participant recall of the previous week, Spearman rank correlation = .57 for voiding frequency and .70 for UI episodes (Brown, 2003; Locher, 2001; Wyman, 1988). For this study, any episode of vaginal discharge or spotting will also be recorded on the diary.

Patient Global Impression of Improvement (PGI-I)

PGI-I is a global rating of improvement using 7-point scale. Construct validity was established in two randomized controlled studies ($n=1,133$ subjects) of drug treatment for predominant stress incontinence (Wagner, 1996; Yalcin, 2003).

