5. APPENDIX E: VOIDING DIARY

VOIDING DIARY

Wake Time: _____

Study ID: _____

Bed Time: _____

Date (m/d/y): _____

Time	Fluid Intake (ounces)	Urine Amount cc's/ml's or ounces (oz)	Leaking (if you leak, first give the episode a "score" in the first column then circle if you think it is stress or urge incontinence, or both in the second column)		Urgency	Pad Replaced	Bowel Movement	Pelvic and/or Bladder/Urinary Related Pain	Vaginal discharge color	Vaginal discharge amount
A: a.m. P: p.m.		Amount Voided	0: None 1: Mild 5: Mod. 10: Severe	S: Stress U: Urge	0: None 1: Mild 5: Mod. 10: Severe	1: Tissue 2: Pantiliner 3: Thick Pad 4: Diaper	N: Normal C: Constipated D: Diarrhea L: Leaking stool	0: None 1: Mild 5: Mod 10: Severe	0: no discharge 1: red 2: brown 3: white 4: yellow	1: Spotting 2: dime size 3: quarter size 5: more than quarter size
5:00 AM				S U						
A P				S U						
A P				S U						
A P				S U						
A P				S U						
A P				S U						
A P				S U						
A P				S U						
A P				S U						
A P				S U						
A P				S U						
A P				S U						
A P				S U						
A P				S U						
A P				S U						
A P				S U						
A P				S U						
A P				S U

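### Volume per void is divided by all recorded voids, so a void logged without a volume counts as 0 ml, and a shift in measuring habits can pass for a change from baseline

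*Combined protocol and SAP*

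**What the plan says.** Section 3.3 lists "Change in urine volume per void from Baseline to Week 12" as the second of twelve secondary endpoints; the first is the change in daily voids. Section 10.1 gives the calculation for each. For volume per void it specifies "summing the total urine amount over the 3 day period and dividing by the total number of voids recorded over 3 days". For frequency: "The average number of voids per day will be calculated by summing the number of voids over the 3 day period and dividing by 3". Both changes are tested with the exact Wilcoxon signed-rank test. The exploratory part of 10.1 repeats the tests at earlier visits and adds a mixed-model slope over all assessment times.

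Section 8 describes the diary: "Subjects will also be asked to record urinary frequency, and urgency. Urine volume will also be recorded". The form in Appendix E has one column for volume, headed "Urine Amount cc's/ml's or ounces (oz" with the sub-heading "Amount Voided". As reproduced, it has no separate mark for a void and no code for a void that was not measured.

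On missing data, Section 10 says "No imputations for missing data will be conducted", and 10.1 repeats this for the exploratory analyses. Section 13.1.1 has blank fields noted as unknown or not applicable. No section says how a void without a volume enters the ratio, or sets a minimum number of measured voids.

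**The concern.** The numerator can hold only volumes that someone measured. The denominator, as worded, holds every void on record. Where the two sets differ, the ratio is no longer a mean volume: each unmeasured void is in effect scored as 0 ml, in a plan that says it imputes nothing.

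Subjects complete four diaries (Baseline and Weeks 4, 8 and 12), so measuring habits have room to improve or lapse. In a randomised trial, similar drift in both arms would largely cancel. Here Section 1 describes a single open-label arm, so drift and drug effect cannot be told apart. Section 10 says volume per void will be weighed when response to treatment is judged. A shift in measuring habits could therefore be read as a change in bladder function, in either direction.

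**Working it through.** The plan states no figure for this endpoint, so there is none to reproduce. The check is algebra on the stated formula, followed by illustrations on assumed values.

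**Algebra.** Let a diary hold *n* recorded voids, *m* of them with a volume, and let *V* be the mean of the measured volumes.

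- Ratio in 10.1: (*m* × *V*) / *n* = *V* × *m*/*n*.
- This equals (*m* × *V* + (*n* − *m*) × 0) / *n*, the mean over all *n* voids with each unmeasured one set to 0 ml.
- With the denominator restricted to measured voids: (*m* × *V*) / *m* = *V*.

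**Shares that differ between visits.** Assume *V* = 200 ml at both visits, so no true change.

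- 20% unmeasured at Baseline: 200 × 0.8 = 160 ml. 10% at Week 12: 200 × 0.9 = 180 ml. Ratio 180/160 = 1.125, a false rise of 12.5%.
- The reverse order: 160/180 = 0.889, a false fall of about 11%.

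**Whole-void counts.** Assume *V* = 200 ml and *n* = 24 voids per three-day diary (8 per day).

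| Measured at Baseline | Measured at Week 12 | Ratio at Baseline (ml) | Ratio at Week 12 (ml) | Change (ml) | Change with restricted denominator (ml) |
|---|---|---|---|---|---|
| 24 | 22 | 200.0 | 183.3 | −16.7 | 0 |
| 24 | 20 | 200.0 | 166.7 | −33.3 | 0 |
| 24 | 18 | 200.0 | 150.0 | −50.0 | 0 |
| 18 | 24 | 150.0 | 200.0 | +50.0 | 0 |
| 18 | 18 | 150.0 | 150.0 | 0 | 0 |

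In the last row the change is right, but both levels are 25% low (150/200 = 0.75), and any true change would also be scaled by 0.75. For 24 then 20 measured, taking *V* from 150 to 250 ml moves the false change from −25.0 to −41.7 ml.

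**Effect on the test.** Simulation with 30 completers (the target in Section 10), 24 voids per diary and no true change. Assumed values: mean 200 ml, SD 50 between subjects, 20 between visits and 80 between voids, and volumes missing at random. The two-sided exact Wilcoxon test at 0.05 was run in 2,000 trials per row.

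| Measured share, Baseline then Week 12 | Mean change, 10.1 ratio (ml) | Rejections, 10.1 ratio | Rejections, restricted denominator |
|---|---|---|---|
| 95% then 95% | 0.1 | 5.2% | 4.9% |
| 95% then 90% | −10.3 | 31.7% | 5.3% |
| 95% then 85% | −20.3 | 79.4% | 4.7% |
| 80% then 95% | +30.5 | 98.6% | 4.7% |

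Each row gives all subjects the same expected share at a visit. Differences in share that go up in some subjects and down in others would mainly add noise.

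**The other counting rule.** Suppose a void is counted only when an amount is entered. Then *n* = *m* and the ratio is *V*, but voids per day shrinks by the unmeasured share. At an assumed true 8 per day, 20% then 10% unmeasured gives 8 × 0.8 = 6.4 then 8 × 0.9 = 7.2, a false rise of 12.5% in the first secondary endpoint. The same drift moves to a different endpoint.

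**The case against.** The strongest reply is that the form defeats the problem. If a void is visible only through the "Amount Voided" column, one without an amount may never be counted as recorded. It then leaves numerator and denominator together, and the ratio is already the mean of measured voids. The no-imputation rule and the coding of blanks as unknown point the same way. This stands in part: it shows that scoring 0 ml is what the formula gives when read literally, not a handling the plan announces. It does not close the gap. Section 8 treats frequency and volume as separate items, no counting rule is written, and this reading passes the loss to voids per day.

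Three stronger readings are tempting and are not supported.

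- A reader might infer that every diary with an unmeasured void yields a wrong value. That depends on the void being counted, which the documents leave open. Appendix E as reproduced also cannot show how subjects were told to log such a void.
- A reader might infer that the error must fail to cancel. It cancels in a zero true change when the measured share is equal at both visits. Section 7.1 has diaries reviewed at the clinic visits, which gives staff a chance to query blanks. Nothing in the documents shows that drift will occur.
- A reader might take the synopsis, "Secondary efficacy measures will include reduction in number of voids per day, volume of voids, 24 hour pad weight", as seeking a fall in both frequency and volume per void, which conflict at constant daily output. The sentence is a loose list whose first noun does not fit later items such as questionnaire responses. Sections 3.3 and 10.1 use the neutral idea of change.

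It is also fair that this is one of twelve secondary endpoints in an unpowered, descriptive study. That limits the consequence but does not make the formula right.

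**Conclusion.** The point holds, with medium confidence. Applied as written, the Section 10.1 ratio is low by the share of recorded voids that lack a volume, and nothing else in the documents restricts the denominator. A false average change also needs that share to shift between visits.

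The size cannot be computed, because no rate of unmeasured voids is given. Under the assumptions above, a move from 20% to 10% unmeasured gives a false rise of 12.5%. In the simulation, a five-point drop in the measured share (95% to 90%) was enough to lift false rejections to about 32%. Under the alternative counting rule the error falls on voids per day. The primary endpoint is untouched.

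**What to change.** In Section 10.1:

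1. Define volume per void as the sum of measured volumes divided by the number of voids with a measured volume.
2. Count every recorded void, measured or not, for voids per day, and state how an unmeasured void is logged. A tick or code on the diary would do this; so would a written rule for rows with no amount.
3. Report the share of voids measured at each visit, so that any drift is visible beside the result.

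The cost is a few sentences and one descriptive line per visit. If diaries are already in use, the denominator and the rule for rows with no amount can still be fixed before analysis. The drawback is that measured voids may not fully represent unmeasured ones, for example if voids away from home differ in volume. That is still a milder assumption than 0 ml, and the reported share shows how much rests on it.
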